12.5 Appendix 5: Best Corrected Visual Acuity (BCVA)

BCVA testing should precede any examination requiring contact with the eye and should precede pupil dilation or instillation of anesthetic eye drops. BCVA testing will be performed following manifest refraction. Subjects will be tested in their right eye first, followed by the left eye.

BCVA will be evaluated in each eye individually using ETDRS charts at a distance of 4 meters and scored on a LogMAR scale. BCVA should be evaluated consistently throughout the study using the same method, equipment, and lighting conditions at each site.

Subjects will be instructed to read the letters on the ETDRS chart from the top left-hand corner along each row, one letter at a time, then down each row, one at a time. There are no numbers on the chart, only letters. If a subject reads a number, the examiner should remind the subject that the chart contains no numbers, and the examiner should then request a letter instead of a number from the subject. Subjects should be encouraged to guess if a letter appears unclear. If a subject identifies a letter as 1 of 2 possible letters, the examiner should ask the subject to pick 1 letter only.

Subjects will be instructed to read slowly at a rate of about 1 letter per second. If at any point the subject reads too quickly, the examiner should stop the subject and remind the subject to read slowly in order to achieve the best identification of each letter. If a subject loses their placement in the chart, the examiner should ask the subject to go back to the line where the place was lost. The subject should not proceed to the next letter until they have given a definite response. If a subject changes a response before moving on to the next letter, the examiner must accept the change. The examiner should circle each correct letter on the VA worksheet and draw a single line through each incorrect letter.

At the end of the test, the examiner will count the number of letters incorrectly identified, up to and including the last line read, and will record the results on the source document. A VA letter score will be calculated and recorded in the source documents and in the eCRF.

Each letter has a score value of 0.02 log units. Since there are 5 letters per line, the total score for a line on the LogMAR chart represents a change of 0.1 log units. The formula used in calculating the score is:

Calculation: LogMAR VA = Baseline value + (n X 0.02)

where: Baseline value is the LogMAR number of the last line read (at least 1 letter read correctly in this line), and
"n" is the total number of letters missed, up to and including the last line read, and
"0.02" is the value for each letter

12.6 Appendix 6: Intraocular Pressure (IOP)

Intraocular pressure measurements (1 measurement per eye) should be conducted after the slit lamp examination is completed and before pupil dilation. This method requires the administration of proparacaine 0.5% to the eye before testing. There should always be ≥ 30 minutes between the administration of topical anesthetic and IP.

IOP measurements should be performed using a Goldmann applanation tonometer, handheld contact tonometer, or pneumatonometer according to the Investigator's standard procedure. The same method of measuring IOP should be used on the same subject at all visits. Non-contact and rebound methods of testing IOP are not permitted.

Measurements should be taken with the subject seated. All pressures should be recorded in mmHg, and measurements should be recorded in the eCRF.

CONFIDENTIAL

12.7 Appendix 7: Dilated Ophthalmoscopy

A dilated fundus examination will be performed after the application of dilating drops (1% tropicamide) and upon the Investigator confirming with a pen light that both eyes are fully dilated after waiting 20 minutes. If the pupils are still responsive to light, an additional drop will be added to each eye, and the Investigator will wait to proceed until the pupils no longer respond to the pen light. Since dilating drops are being applied, the fundus examination must be performed after visual acuity, IOP, and slit lamp examination.

The evaluation will include assessment of the vitreous, retina, macula, choroid, optic nerve, and optic nerve cup-to-disc ratio. After the procedure, the Investigator will determine if findings are within normal limits or are abnormal. Only shifts from Normal to Abnormal, Clinically Significant, or from Abnormal, Not Clinically Significant, to Abnormal, Clinically Significant, will be recorded as AEs.

Vitreous	Normal: Absence of any opacity Abnormal: Presence of opacity Not Clinically Significant Clinically Significant If Abnormal, Clinically Significant, specify: _____
Retina	Normal: Absence of active inflammation or significant structural changes Abnormal: Presence of active inflammatory signs or significant structural changes Not Clinically Significant Clinically Significant If Abnormal, Clinically Significant, specify: _____
Macula	Normal: Absence of active inflammation or significant structural changes Abnormal: Presence of active inflammatory signs or significant structural changes Not Clinically Significant Clinically Significant If Abnormal, Clinically Significant, specify: _____
Choroid	Normal: Absence of active inflammation or significant structural changes Abnormal: Presence of active inflammatory signs or significant structural changes Not Clinically Significant Clinically Significant If Abnormal, Clinically Significant, specify: _____
Optic Nerve	Normal: Absence of any damage Abnormal: Presence of any damage Not Clinically Significant Clinically Significant If Abnormal, Clinically Significant, specify: _____
Cup-to-Disc Ratio	Vertical Optic Nerve Cup-to-Disc Ratio: _____. _____. Horizontal Optic Nerve Cup-to-Disc Ratio: _____. _____. Indicate any other dilated fundus ophthalmoscopy findings:
Other	Normal Abnormal Not Clinically Significant Clinically Significant If Abnormal, Clinically Significant, specify: _____

CONFIDENTIAL

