8.2.1 Adverse Events and Serious Adverse Events

AEs will be monitored throughout the study. Subjects will be encouraged to report any adverse findings during the study, whether or not they are related to IP. These can be collected either in an unsolicited fashion without any prompting or in response to a general question such as: “Have you noticed anything different since you started the study; began the IP, etc.?”

CONFIDENTIAL

All AEs will be captured on the appropriate source documents and recorded in the eCRF. Information to be collected at minimum includes event description, onset, assessment of severity, relationship to IP, and outcome.

The Investigator will record all AEs with start dates occurring any time after informed consent is obtained until 7 (for nonserious AEs) or 30 days (for SAEs) after the last day of study participation. At each visit, the Investigator will inquire about the occurrence of AEs/SAEs since the last visit. SAEs will be followed for outcome information until resolution or stabilization.

Any medical condition that is present at the time that the subject is screened will be considered as baseline and not reported as an AE. However, if the subject's condition deteriorates at any time during the study, it will be recorded as an AE.

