8.2.1.1 Definitions

An AE is any untoward medical occurrence in a subject temporally associated with the use of IP, whether or not considered related to the IP. An AE can therefore be any unfavorable and unintended sign (including an abnormal laboratory finding), symptom, or disease (new or exacerbated) temporally associated with the use of IP without any judgment on causality.

An AE is considered "serious" if it:

- Results in death
- Is a life-threatening AE

Note: An AE is "life-threatening" if, in the view of the Investigator or Sponsor, its occurrence places the subject at immediate risk of death. It does not include an AE that, had it occurred in a more severe form, might have caused death

- Requires inpatient hospitalization or prolongation of existing hospitalization
- Results in persistent or significant incapacity or substantial disruption of the ability to conduct normal life functions
- Is a congenital anomaly or birth defect

Important medical events that may not result in death, be life-threatening, or require hospitalization may be considered serious when, based upon appropriate medical judgment, they may jeopardize the subject and may require medical or surgical intervention to prevent one of these outcomes.

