#### **9.7.1.6.4. Dilated Ophthalmoscopy (Fundus Exam)**

The frequency and percentage of subjects with observed values of each category as well as the categorical shift from baseline at each post-baseline visit will be tabulated at each scheduled visit for the study eye and non-study eye. The percentages are calculated based on the number of subjects at each visit in each treatment group based on non-missing observations of the Safety Analysis Set. The percentages for the shift will be calculated based on the number of subjects with both baseline and post-baseline values.

Descriptive summaries of the observed cup-to-disc ratio at each scheduled visit as well as the change from baseline at each post-baseline visit will be presented for both eyes.

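### The fundus-specific AE rule conflicts with the general deterioration rule, so worsening that stays within one grading category may go unrecorded as an AE and does not show in the shift table

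*Protocol*

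**What the plan says.** **Fundus rule.** Protocol Appendix 7 grades each fundus structure as Normal, Abnormal Not Clinically Significant (NCS) or Abnormal Clinically Significant (CS). It then states: "Only shifts from Normal to Abnormal, Clinically Significant, or from Abnormal, Not Clinically Significant, to Abnormal, Clinically Significant, will be recorded as AEs". SAP 9.5.1.4.6 repeats this sentence.

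**General rule.** Protocol 8.2.1 treats a condition present at screening as baseline, but adds: "if the subject's condition deteriorates at any time during the study, it will be recorded as an AE". SAP 9.5.1.4.1 repeats it. The AE definition in Protocol 8.2.1.1 points the same way, since it covers "disease (new or exacerbated) temporally associated with the use of IP without any judgment on causality".

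**Detail within a category.** The form has no severity grade inside CS. It offers only a free-text line: "If Abnormal, Clinically Significant, specify".

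**Planned tables.** For fundus findings, SAP 9.7.1.6.4 tabulates observed categories and says that "the categorical shift from baseline at each post-baseline visit will be tabulated at each scheduled visit for the study eye and non-study eye". The same section adds "Descriptive summaries of the observed cup-to-disc ratio at each scheduled visit" and the change from baseline, for both eyes.

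**Timing.** In the schedules of both documents, dilated ophthalmoscopy is done at Visits 1 and 7 only.

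**The concern.** Take a macular or retinal finding graded CS at Visit 1 that is plainly worse at Visit 7. Under Protocol 8.2.1 it is an AE. Under Appendix 7, read literally, it is not, because no listed shift has occurred. The same holds for an NCS finding that worsens but stays NCS.

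Safety is the trial's secondary objective, and dilated ophthalmoscopy is one of its named safety assessments. If sites differ in which instruction they follow, the same event may be recorded at one site and not at another. Any error runs in one direction, towards under-recording. The restriction is also peculiar to the fundus. The slit lamp appendix (Appendix 3) has no such rule and exempts only the planned change from phakic to pseudophakic. Worsening of a significant iris finding is therefore an AE, while worsening of a significant macular finding is arguably not.

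**Working it through.** The point rests on no figure, so there is nothing to recompute. The check sets the rules side by side and runs every non-improving transition on the three-level scale through them.

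**Inputs**
- AE rule for the fundus: Protocol Appendix 7; SAP 9.5.1.4.6.
- AE rule for existing conditions: Protocol 8.2.1; SAP 9.5.1.4.1.
- AE definition: Protocol 8.2.1.1.
- Shift table: SAP 9.7.1.6.4.
- Baseline: SAP 9.7.1 takes the last measurement before dosing, which for the fundus is Visit 1.

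| Visit 1 to Visit 7 | AE under Appendix 7? | Visible in the shift table? |
|---|---|---|
| Normal to NCS | No | Yes |
| Normal to CS | Yes | Yes |
| NCS to CS | Yes | Yes |
| NCS to worse NCS | No | No |
| CS to worse CS | No | No |

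In the last two rows a finding present at screening has deteriorated, so Protocol 8.2.1 would make each an AE. Appendix 7 does not list them, and the shift table counts them in the unchanged NCS/NCS or CS/CS cell. These two rows are the gap.

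**Other routes to the report**
- Listings: SAP 9.7.1 lists all collected data, including the free text for CS findings.
- Cup-to-disc ratio: change from baseline is summarised (SAP 9.7.1.6.4). This helps only if the worsening alters that ratio.
- Visual acuity: LogMAR change and loss of 3 or more ETDRS lines are summarised for both eyes (SAP 9.7.1.6.6). This helps only if the worsening lowers acuity.
- Another structure: vitreous, retina, macula, choroid and optic nerve are graded separately, so worsening that newly involves a second structure can appear as a shift there.

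What remains is worsening within the same structure and category that changes neither acuity nor cup-to-disc ratio. Where Appendix 7 is followed, it reaches listings but no summary table.

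**Who can enter with such a finding**
- Study eye: inclusion 4 (clear media apart from cataract) and exclusion 9 (pathology that may affect acuity) make a significant baseline finding uncommon.
- Either eye: exclusions 5 and 6 remove inflammatory eye disease and intraocular inflammation.
- Subject level: exclusion 23 names suspected glaucoma and glaucomatous fundus changes.
- Non-study eye: inclusion 4 and exclusion 9 do not apply, and inclusion 7 expressly refers to pathology other than cataract. Safety is reported for this eye too (SAP 9.7.1.1.2 and 9.7.1.6).

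**The case against.** The best defence is that Appendix 7 only says which *category shifts* count as AEs, so as to keep Normal to NCS out of the AE record. Worsening inside a category is not a shift, so the sentence would be silent on it and 8.2.1 would apply. This reading is possible but strained. The sentence opens with *Only*, it is the more specific instruction, and it sits in the appendix on that examination. Nothing in either document says that 8.2.1 still applies beside it. Protocol 10.1.8 mentions a Manual of Procedures that might settle the matter, but it is not among the documents.

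Three further objections stand and limit the point:
- The loss is conditional. A site that follows 8.2.1 records the event. Sites also ask about AEs at every visit, so symptomatic worsening need not wait for Visit 7.
- A reader might infer that the AE record is the only way such worsening could reach the safety output. The documents do not support that, given the listings and the cup-to-disc and acuity summaries.
- The eyes most likely to be affected are non-study eyes, which are not dosed under the protocol (5.1.2 directs the drop to the study eye).

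**Conclusion.** The conflict is real and appears in both documents. Its consequence is conditional: where Appendix 7 is followed literally, same-category worsening of a fundus finding present at Visit 1 is not recorded as an AE and cannot be seen in the shift table. Both CS to worse CS and NCS to worse NCS are affected.

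The size is small. The entry criteria limit baseline fundus pathology in study eyes, so the gap mainly concerns non-study eyes. A reader might infer a number of missed events, but the documents give neither the frequency of baseline fundus findings nor a rate of worsening, so no count is supported. Nor do they show that sites actually diverged, only that the text allows it. No efficacy analysis is affected. This is a minor clarification worth making, not a threat to the trial's conclusions.

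**What to change.** Reconcile Protocol Appendix 7 and SAP 9.5.1.4.6 with Protocol 8.2.1 and SAP 9.5.1.4.1. Keep the shift rule and add one sentence after it, for example: *This rule does not override Section 8.2.1; deterioration of a fundus finding present at Visit 1 is also recorded as an AE, even when its category does not change.* In the SAP, the cross-reference would be to 9.5.1.4.1.

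This covers both same-category cases. It is better than simply deleting *Only*, which would weaken the evident purpose of keeping new non-significant findings out of the AE record.

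The cost is one sentence in each document and a few more AEs to record. No examination or table is added.

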12.8 Appendix 8: Compliance Statement

The study will be conducted in accordance with International Council for Harmonisation Good Clinical Practice (ICH GCP), with the United States (US) Code of Federal Regulations (CFR) applicable to clinical studies (45 CFR Part 46, 21 CFR Part 50, 21 CFR Part 56, 21 CFR Part 312, and/or 21 CFR Part 812), and as stipulated in the Declaration of Helsinki with respect to the use of human subjects in clinical studies and investigations.

CONFIDENTIAL

### LIST OF ABBREVIATIONS AND DEFINITIONS OF TERMS

ACC	Anterior Chamber Cell
ACF	Anterior Chamber Flare
AE	Adverse Event
API	Active Pharmaceutical Ingredient
ATC	Anatomical Therapeutic Chemical Classification
BCVA	Best Corrected Visual Acuity
CELR	Cataract Extraction And Lens Replacement
CFB	Change From Baseline
CRF	Case Report Form
Ecrf	Electronic Case Report Form
ETDRS	Early Treatment Diabetic Retinopathy Study
FAS	Full Analysis Set
GCP	Good Clinical Practice
GLP	Good Laboratory Practice
GMP	Good Manufacturing Practice
IOP	Intraocular Pressure
IP	Investigational Product
MMRM	Mixed-Effect Repeated Measures
NPRS	Numeric Pain Rating Scale
OD	Right Eye
OS	Left Eye
OU	Both Eyes
PP	Per Protocol
PT	Preferred Term
QID	Four Times A Day
SAE	Serious Adverse Event
SAF	Safety Analysis Set
SAP	Statistical Analysis Plan

SD	Standard Deviation
SOC	System Organ Class
SUN	Standardization Of Uveitis Nomenclature
TEAE	Treatment-Emergent Adverse Events
US	United States
WHODRUG	World Health Organization Drug Dictionary
WOCBP	Women Of Childbearing Potential

## PROTOCOL SYNOPSIS

Title:	A phase 2, double-masked, randomized, vehicle-controlled study of VVN461 Ophthalmic Solution in treating post-operative ocular inflammation in subjects undergoing routine unilateral cataract surgery
Phase:	2
Design/Conduct:	This is a multicenter, double-masked, randomized, vehicle-controlled, parallel comparison study conducted at sites in the United States (US) in subjects undergoing routine unilateral cataract extraction and lens replacement (CELR) surgery via phacoemulsification
Objectives:	Primary: Evaluate the ocular efficacy of 2 different doses of VVN461 Ophthalmic Solution in treating post-operative ocular inflammation associated with cataract surgery compared with the ocular efficacy of a matching Vehicle Secondary: Evaluate the safety of VVN461
Endpoints:	Primary Endpoint: 

Proportion of subjects with anterior chamber cell (ACC) Grade 0 in the study eye at Visit 6 (Day 14)

 Secondary Endpoints: 

Proportion of subjects with ACC Grade 0 in the study eye at Visit 5 (Day 7)

Proportion of subjects with anterior chamber flare (ACF) Grade 0 in the study eye at Visit 6 (Day 14)

Proportion of subjects with ACF Grade 0 in the study eye at Visit 5 (Day 7)

Proportion of subjects requiring rescue medication before Visit 6 (Day 14)

 Exploratory Endpoints: 

Mean change from baseline (CFB) in ACC Grade in the study eye at each visit

Mean CFB in ACF Grade in the study eye at each visit

Proportion of subjects with no post-operative ocular pain in the study eye at Visit 6 (Day 14)

Proportion of subjects with no post-operative ocular pain in the study eye at Visit 5 (Day 7)

Population Studied:	Approximately 90 completed subjects (30 per group) who have undergone routine unilateral CELR surgery via phacoemulsification without surgical complication. Subjects who meet all inclusion criteria will be eligible for study participation.

	
Inclusion Criteria:
 

1. <math>\geq 21</math> years of age and in good general health at Visit 1 (Screening)

2. Willing and able to provide informed consent and provide relevant privacy authorization(s)

3. Willing and able to comply with study requirements and visit schedule

4. Clear ocular media (other than cataract) in the study eye

5. Planning to undergo routine unilateral CELR surgery via phacoemulsification extraction and implantation of an intraocular lens.

 
Allowed in the study eye at Visit 2 (Day of Surgery):
 

a. Limbal relaxing incisions (laser-assisted and non-laser)

b. Intracameral injections and intracameral medications, excluding those identified in Exclusion Criterion #2

 

6. At Visit 1 (Screening), has pinhole best corrected visual acuity (BCVA) <math>\leq 0.2</math> Logarithm of the Minimum Angle of Resolution (LogMAR) (i.e., 20/32 Snellen) in the study eye as assessed using Early Treatment Diabetic Retinopathy Study (ETDRS)

7. At Visit 1 (Screening), has BCVA <math>\leq 1.0</math> LogMAR (i.e., 20/200 Snellen) in the non-study eye due to pathology other than cataract as assessed using ETDRS

8. Able to self-administer eye drops

9. At Visit 3 (Baseline/Randomization; Day 1), has ACC Grade <math>\geq 2</math> in the study eye

 
Subjects who meet any of the following exclusion criteria will not be eligible for study participation.
 
Exclusion Criteria:
 
Ophthalmic (Either Eye)
 

1. Any ocular pain at Visit 1 (Screening)

2. Used within 1 week before Visit 1 (Screening), or be planning to use during the study, corticosteroids, oral or topical non-steroidal antiinflammatory drugs (NSAIDs), or Omidria® (i.e., phenylephrine and ketorolac injection)

3. Moderate to severe lid, conjunctival, or corneal findings at Visit 1 (Screening)

4. Corneal abnormality (e.g., stromal, epithelial, or endothelial dystrophies, including epithelial basement membrane dystrophy)

5. History of chronic/recurrent inflammatory eye disease (e.g., scleritis, any uveitis, herpes keratitis)

6. Any signs of intraocular inflammation (cell/flare) at Visit 1 (Screening)

7. Intraocular pressure (IOP) <math>\geq 24</math> mmHg at Visit 1 (Screening)

--	---

	
Ophthalmic (Study Eye)
 

8. Using or unwilling to forgo contact lens use within defined windows before Visit 2 (Day of Surgery) and for the duration of the study

a. Polymethyl methacrylate contact lenses (6 months before surgery and throughout study)

b. Gas permeable rigid lenses (1 month before surgery and throughout study)

c. Extended wear or daily soft lenses (7 days before surgery and throughout study)

9. Known pathology that may affect visual acuity, particularly retinal changes that affect vision (e.g., macular degeneration, cystoid macular edema, proliferative diabetic retinopathy)

10. Capsule or zonular abnormalities with pre-operative crystalline lens tilt or decentration (e.g., Marfan's syndrome) or abnormalities that may affect post-operative centration or tilt of the crystalline lens (e.g., pseudoexfoliation syndrome)

11. History of moderate to severe ocular trauma with the possibility of previous zonule dehiscence

12. Ocular or periocular surgical interventions within defined windows before Visit 1 (Screening)

a. Microinvasive glaucoma surgery, any incisional ocular surgery, or intracameral drug depot to lower IOP (any history)

b. Intraocular surgery (6 months)

c. Laser surgery, limbal relaxing incision procedure, eyelid surgery (3 months)

13. Pupil abnormalities (e.g., non-reactive, tonic pupils, abnormally shaped pupils, pupils that do not dilate at least 3.5 mm under mesopic/scotopic conditions)

14. Keratoconus or significant irregular astigmatism on pre-operative ocular topography

15. Have a condition, or be in a situation, that may put the subject at significant risk of complex surgery and surgical complications that would lead to withdrawal from the study

 
Ophthalmic (Non-study Eye)
 

16. Underwent cataract surgery <14 days before Visit 1 (Screening) or, during the study, will require cataract surgery <1 day after Visit 2 (Day of Surgery)

 
General
 

17. Within 30 days before Visit 1 (Screening), participated in an investigational drug or device study, or have used an investigational drug or device

--	---

	
 
18. Allergy or hypersensitivity to the investigational product (IP) or its excipients
 
19. Significant systemic disease (e.g., uncontrolled diabetes; myasthenia gravis; hepatic, renal, cardiovascular, or endocrine disorders)
 
20. Uncontrolled systemic disease, defined as, within 30 days before Visit 1 (Screening), a change in disease status or medications that may put the subject at increased risk or confound interpretation of study results
 
21. Changes within 30 days before Visit 1 (Screening), or anticipated changes during the study, to the dosage of systemic medication that could have a substantial effect on IOP
 
22. Known bleeding tendencies
 
23. Acute or chronic disease or illness that would put the subject at increased risk or confound interpretation of study results (e.g., autoimmune disease, connective tissue disease, immunodeficiency, suspected glaucoma, glaucomatous changes in the fundus or visual field, ocular inflammation, etc.)
 
24. Requires, is likely to require, or is unwilling to discontinue the use of prohibited medications
 
25. Pregnant, nursing, or planning a pregnancy during the study
 
26. Unwilling or unable to use an acceptable method of contraception throughout the study if a woman of childbearing potential (WOCBP)
 
27. Unwilling or unable to use an acceptable method of contraception throughout the study if a male sexual partner of a WOCBP
 

Investigational Products:	
 
• VVN461, 1.0%
 
• VVN461, 0.5%
 
• Vehicle
 

Dosing Regimen:	Approximately 90 completed subjects will be randomized in a 1:1:1 ratio to VVN461, 1.0%, VVN461, 0.5%, or a matching Vehicle that does not contain the active pharmaceutical ingredient (API). Subjects will administer 1 eye drop in the study eye four times a day (QID) for 14 days.
Assessments/Evaluations:	
Efficacy:
 
 
• Ocular inflammation (Standardization of Uveitis Nomenclature [SUN] Scale)
 
• Post-operative ocular pain (Numeric Pain Rating Scale [NPRS])
 
 
Safety:
 
 
• Adverse event (AE) monitoring (ocular and non-ocular)
 
• Clinically relevant changes from baseline in the following: 
 
▪ BCVA
 
▪ Slit lamp biomicroscopy
 
▪ IOP
 
▪ Dilated ophthalmoscopy
 
 
 

Duration of Study:	Subjects will be assessed at 7 visits over approximately 8 weeks. Visits will include a screening visit, the day of cataract surgery, a baseline/randomization visit, and efficacy and safety evaluation visits after 3, 7, and 14 days of QID dosing with IP in the study eye. The study will conclude with a safety follow-up visit approximately 1 week after the end of the planned dosing period.
Statistical Methods:	
A sample size of approximately 90 completed subjects will be randomized in a 1:1:1 ratio to VVN461, 1.0%, VVN461, 0.5%, and a matching Vehicle that does not contain the API. With a sample size in each group of 30, the study will have 80% power to detect a difference of 35%, assuming a response rate of 30% in the Vehicle group, and a two-sided 0.05 significance level for a Pearson chi-square test. A drop-out rate of 10% is assumed, resulting in a total sample size of approximately 102 subjects.
 
The Full Analysis Set (FAS) will consist of all subjects who are randomized. Subjects will be analyzed in the group to which they are randomized. This set will be used for the analysis of all efficacy endpoints as the primary analysis.
 
The Per Protocol (PP) Analysis Set is a subset of the FAS and will include all subjects in the FAS who complete study-required treatment and who follow the protocol without significant deviations. The determination of significant protocol deviations will be made before database lock and unmasking.
 
The Safety Analysis Set (SAF) will include all subjects who receive at least one dose of IP, as indicated on the dosing record. Subjects will be analyzed in the group according to the treatment received. All safety variables will be analyzed using the SAF, and only observed data will be included (i.e., missing data will remain missing for the safety analysis).
 
Primary Estimand: The primary estimand is treatment difference between VVN461 (1.0% or 0.5%) and the Vehicle in the proportion of subjects with ACC Grade 0 at Visit 6 (Day 14) in the study eye using the FAS.
 
Target Population: Subjects undergoing routine cataract surgery who meet the study entry criteria.
 
Endpoint: Proportion of subjects with ACC Grade 0 in the study eye at Visit 6 (Day 14).
 
Treatment Condition(s): Treatment condition is based on randomized treatment.
 
Population-level Summary: The difference in proportions in subjects with ACC Grade 0 in the study eye at Visit 6 (Day 14) and the corresponding p-value.

	
The proposed procedures to handle missing data and intercurrent events are as follows:
 

• Discontinuation of study therapy with continued participation in the study without receipt of rescue therapy

◦ Treatment Policy Approach – no imputation; use observed data

• Receipt of rescue therapy (topical corticosteroid) in the study eye

◦ Composite Approach – subjects who receive rescue therapy at or before the assessment visit will be assumed to have failed the primary endpoint

• Missing data with or without withdrawal, regardless of reason

◦ Hypothetical Approach – no imputation; analysis will be based on subjects who have an evaluable anterior chamber in the study eye at Visit 6 (Day 14)

 
Pearson's chi-square will be used to test the primary endpoint between the 2 different doses of VVN461 versus the Vehicle. The primary analysis will also be performed on the PP Analysis Set.
 
The secondary efficacy endpoints will include the proportion of subjects with ACC Grade 0, the proportion of subjects with ACF Grade 0, and the proportion of subjects requiring rescue medication. These endpoints will be analyzed regardless of the significance of the primary endpoint analysis. Secondary efficacy comparisons with p-values that claim statistical significance should be understood to be "nominal," as they will not be adjusted for multiplicity.
 
Exploratory endpoints will be analyzed in a manner similar to the secondary endpoints. Mean CFB in ACC Grade and ACF Grade will be analyzed using mixed model repeated measures. The model will include treatment, visit, and treatment by visit interaction as fixed effects and a covariate for baseline measurement (where appropriate) with a random effect for site. An unstructured covariance among repeated measurements will be assumed. Only data from before the use of rescue medication will be included in these analyses. The proportion of subjects with no post-operative ocular pain in the study eye at Visit 5 (Day 7) and Visit 6 (Day 14) will also be analyzed. Exploratory efficacy comparisons with p-values that claim statistical significance should be understood to be "nominal," as they will not be adjusted for multiplicity.
 
Safety analyses will be performed on all subjects in the SAF. The assessment of safety will be based on the summary of ocular and non-ocular AEs, BCVA, and ophthalmic examinations using slit lamp biomicroscopy and dilated ophthalmoscopy. Summaries will be provided by treatment group and, for ocular assessments, separately by eye.

--	---

